9.8 Additional Research

Additional research related to the study intervention and/or disease may be performed. The results of this additional research could help to improve the diagnosis and/or the treatment of this disease in the future. This research [REDACTED]

9.9 Other Assessments

Not applicable.

9.10 Healthcare Resource Utilization

Healthcare resource utilization data associated with medical encounters will be collected in the eCRF by the investigator and study site personnel for all participants throughout the study (see [Table 2-1](#) and [Table 2-2](#)). Protocol-mandated procedures, tests, and encounters will be excluded.

The data collected may be used to conduct exploratory economic analyses and will include:

- Number and duration of medical care encounters [REDACTED], including surgeries and other selected procedures (inpatient and outpatient).
- Duration of hospitalization (total length of stay in days, including duration by wards; eg, intensive care unit).

10 STATISTICAL CONSIDERATIONS

10.1 Statistical Hypotheses

Due to the open-label design of the study and the lack of a control group, all data will be summarized, and no hypothesis testing will be performed.

10.2 Sample Size Determination

The sample size for this study is not based on statistical power for comparisons among treatment cohorts; it has been selected to minimize the width of the 95% confidence interval (CI) of the estimate of the clinical response rate (primary endpoint) for each cohort.

An estimated total of 250 participants will be enrolled to achieve a total sample of 150 treated participants in Cohort 1, and approximately 165 participants will be enrolled to achieve a total sample of 100 treated participants in Cohort 2. The methods for determining each cohort's sample size are described below.

Cohort 1 (Advanced Therapy-naïve Cohort)

Due to the lack of published data evaluating the proportion of subjects achieving clinical response at Week 12, sample size estimates are based on clinical response rates at Week 10 in the biologic-naïve population from Study RPC01-3101 (ie, patients who have not been exposed to at least one biologic prior to study entry). Based on those results, it is anticipated that at least 50% of Cohort 1 will achieve clinical response at Week 12. Under these assumptions, a sample size of 150 participants would estimate exact binomial 95% CIs ranging between 41.7% and 58.3%.

Cohort 2 (Advanced Therapy-exposed Cohort)

The proportion of patients with clinical response in Cohort 2 is estimated to be 35% to 45% at Week 26 based on the clinical response rate at Weeks 10 and 52, as well as symptomatic response (as a surrogate variable) in the biologic-exposed population of Study RPC01-3101 (ie, patients who have been exposed to at least one biologic prior to study entry). Assuming a 45% clinical response rate at Week 26, a sample size of 100 participants is needed to provide a half-width of

the 95% CI of 10.5% (ie, 95% CI: 35%, 55.3%) using the exact CI formula for binomial probabilities.

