10.4.3 Primary Endpoint

The primary endpoint for each cohort, their corresponding descriptions, and prespecified time points are listed in Table 10.4.3-1.

The primary endpoint for Cohort 1 is the proportion of participants who achieve a clinical response at Week 12. The clinical response rate at Week 12 will be estimated, and the corresponding 95% CI will be derived based on the Clopper Pearson method.

The primary endpoint for Cohort 2 is the proportion of participants who achieve a clinical response at Week 26. An estimate of the clinical response rate at Week 26 will be provided, along with the corresponding 95% CI derived based on the Clopper Pearson method.

For proportion-based efficacy endpoints, patients with missing Week 12 efficacy data from Cohort 1 and/or participants with missing Week 26 efficacy data from Cohort 2 will be considered non-responders, and non-responder imputation will be used. Sensitivity analyses around missing data may involve missing data imputed using multiple imputation and may analyze observed cases with no imputation. Details of the sensitivity analysis will be provided in the SAP.

For continuous efficacy endpoints, observed cases will be analyzed with no imputation.

Table 10.4.3-1: Endpoints

Primary	Description	Timeframe
Clinical Response (modified Mayo score)	Proportion of participants achieving the following: 
Decrease from baseline in the modified Mayo score of ≥ 2 points, andDecrease from baseline in the modified Mayo score of $\geq 35\%$, andDecrease in RB subscore of ≥ 1 point or absolute RB subscore ≤ 1.	Week 12 (Cohort 1) Week 26 (Cohort 2)
Secondary	Description	Timeframe
Clinical Remission (modified Mayo score)	Proportion of treated participants achieving the following in each component of the modified Mayo score: 
SF subscore ≤ 1, with ≥ 1-point decrease from baseline, andRB subscore = 0, andES ≤ 1.	Week 12 (Cohort 1) Week 26 (Cohort 2)
Endoscopic Response	Proportion of treated participants with a decrease from baseline of ≥ 1 point in Mayo ES	Week 12 (Cohort 1) Week 26 (Cohort 2)
Endoscopic Improvement	Proportion of treated participants with Mayo ES ≤ 1	Week 12 (Cohort 1) Week 26 (Cohort 2)

Table 10.4.3-1: Endpoints

Endoscopic Remission	Proportion of treated participants with Mayo ES = 0	Week 26 (Cohort 2)
IBDQ Response	Proportion of participants with a change from baseline in total score of ≥ 16 points	Week 12 (Cohort 1)

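### The 10.5% half-width stated for Cohort 2 is wrong: 100 participants at a 45% response give an exact half-width of 10.1%, and 10.5% needs only 94

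*Combined protocol and SAP*

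**What the plan says.** Section 10.2 (Sample Size Determination) sets power aside and says of the sample size that "it has been selected to minimize the width of the 95% confidence interval (CI") for the response rate in each cohort. For Cohort 2 it gives a planning range: "The proportion of patients with clinical response in Cohort 2 is estimated to be 35% to 45% at Week 26". It then takes the upper end of that range ("Assuming a 45% clinical response rate at Week 26") and makes its claim of need in these words: "a sample size of 100 participants is needed to provide a half-width of". The figure attached to that claim, together with its interval and method, reads "the 95% CI of 10.5% (ie, 95% CI: 35%, 55.3%) using the exact CI formula for binomial probabilities".

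Section 10.4.3 (Primary Endpoint) names the exact method for the analysis: the Cohort 2 response rate will be reported "along with the corresponding 95% CI derived based on the Clopper Pearson method". Treated participants with missing Week 26 data "will be considered non-responders, and non-responder imputation will be used", so the denominator remains all treated participants and no dropout allowance enters the calculation.

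The Protocol Summary repeats the target of 100 treated participants and the precision rationale, but gives no half-width.

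**The concern.** The sentence states precision twice, once as a half-width and once as an interval, and the two disagree. It also says that 100 participants are required to reach the stated half-width. If the half-width is wrong for that number, the claim of need fails with it.

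This matters because Section 10.1 rules out hypothesis testing, which leaves interval width as the only quantitative reason given for the Cohort 2 size. A reader who recomputes the sentence cannot tell from it whether the half-width, the interval or the sample size is the intended figure. Section 10.4 defers detailed methodology to the SAP, so an uncorrected figure could be carried forward into the SAP and the study report.

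**Working it through.** **Inputs.** From Section 10.2: 95% two-sided exact binomial interval, n = 100, assumed response 45% (x = 45), planning range 35% to 45%, stated half-width 10.5%, stated interval 35% to 55.3%. From Section 10.4.3: the exact method is Clopper-Pearson.

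**Formulas.** Lower limit L = 0.025 quantile of Beta(x, n − x + 1). Upper limit U = 0.975 quantile of Beta(x + 1, n − x). Half-width = (U − L)/2.

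**Step 1: check the method on Cohort 1.** For 75/150, L = 41.74% and U = 58.26%. Section 10.2 gives 41.7% to 58.3%, so the method reproduces the plan's own Cohort 1 figures.

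**Step 2: the printed Cohort 2 figures against each other.** (55.3 − 35)/2 = 10.15, not 10.5.

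**Step 3: recompute Cohort 2.** For 45/100, L = 35.03% and U = 55.27%, so the half-width is (55.27 − 35.03)/2 = 10.12. The printed interval reproduces. The printed half-width does not.

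**Step 4: look for any reading that gives 10.5 at n = 100.**

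| Quantity at n = 100 | Value (points) |
|---|---|
| Exact half-width, 35/100 (25.7% to 45.2%) | 9.73 |
| Exact half-width, 40/100 | 9.98 |
| Exact half-width, 45/100 | 10.12 |
| Exact half-width, 50/100 (maximum over all outcomes) | 10.17 |
| Longer (upper) arm of the exact interval, 45/100 | 10.27 |
| Expected exact half-width at a true rate of 45% | 10.07 |
| Wald, 45% | 9.75 |
| Wald with continuity correction, 45% | 10.25 |
| Wilson, 45% | 9.57 |
| Wilson with continuity correction, 45% | 10.05 |

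None reaches 10.5. Rounding does not explain it either: to one decimal, 10.12 is 10.1.

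**Step 5: the n that 10.5 would require.** Exact half-width at 45%:

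| n | x = 0.45n | x rounded to an integer |
|---|---|---|
| 93 | 10.502 | 10.506 (x = 42) |
| 94 | 10.445 | 10.439 (x = 42) |
| 100 | 10.120 | 10.120 (x = 45) |

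The smallest n with a half-width of 10.5 or less is 94, although 93 misses only in the third decimal. Other definitions give other answers, none of them 100:

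- Wald: 1.96² × 0.45 × 0.55 / 0.105² = 86.2, so 87.
- Expected exact half-width: 93 (10.506 at n = 92, 10.449 at n = 93).
- Longer arm of the exact interval: 96 (10.49).

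**Size of the discrepancy.** 10.5 − 10.12 = 0.38 points, and 0.38/10.12 is about 4%. In participants, (100 − 94)/100 = 6%.

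**The case against.** The strongest reply is that almost everything in the sentence is right. The 45% assumption, the 100 participants, the exact method and the printed interval all agree, and a reader has the correct interval in the same parenthesis. The error is also conservative, because true precision is slightly better than stated. No hypothesis test, enrolment number or analysis uses the 10.5%, and the reported interval will be computed from the observed data.

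A second reply is that 94 should not be read as the real design target. Section 10.2 does not present 10.5% as a threshold to be met. The Document History records that Cohort 2 was cut from 150 to 100, and the stated rationale is operational feasibility. The printed interval also fits 100 better than 94: with 94 participants, 42 responders give 34.4% to 55.3% and 43 give 35.4% to 56.3%. A slip for 10.15 is plausible, although the plan does not say so.

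A third reply is that leaving out the 35% case is not an error. The plan used the end of its range with the wider exact interval (10.12 against 9.73), which is the cautious choice for precision.

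All three replies stand as limits on the consequence. None of them makes 10.5% correct or makes 100 participants necessary for it. The figure of 94 shows only that the claim of need is false; it is not a case for enrolling fewer.

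**Conclusion.** The concern holds. With 100 participants and a 45% response, the exact 95% half-width is 10.1 points (10.12), not 10.5. The stated figure contradicts both the interval printed beside it and the method the plan names, and no outcome at n = 100 produces it. The statement that 100 participants are needed for 10.5 is also false, since 94 are enough.

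The conclusion rests on the usual definition of half-width as half the distance between the limits, and on Clopper-Pearson as the exact method, which Section 10.4.3 names. The first part does not depend on the definition, as none of the alternatives tried gives 10.5 at n = 100.

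The practical effect is small and conservative, and the sample size itself is not called into question. The correction should be made because the wrong figure sits in the only sentence that justifies the Cohort 2 size quantitatively.

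**What to change.** Keep N = 100 and the printed interval. In Section 10.2, replace the Cohort 2 statement with wording such as:

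> With 100 treated participants and an assumed Week 26 clinical response of 45%, the exact (Clopper-Pearson) 95% CI would run from 35.0% to 55.3%, a half-width of about 10.1 percentage points.

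This corrects the half-width and drops the claim that 100 is the number required. Optionally, add the lower end of the planning range: at 35% the interval would run from 25.7% to 45.2%, a half-width of about 9.7 points. Carry the same figures into the SAP.

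The cost is one sentence, which can go into the next amendment. Enrolment, endpoints and analyses do not change.

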10.3 Analysis Sets

For the purposes of analysis, the populations are defined as follows:

Population	Description
Enrolled	All participants who signed an ICF and were registered into IRT.
Cohort 1 Treated Analysis Population	All Cohort 1 participants who received at least one dose of study intervention. This population will be used for both the efficacy and safety analyses for Cohort 1.
Cohort 2 Treated Analysis Population	All Cohort 2 participants who received at least one dose of study intervention. This population will be used for both the efficacy and safety analyses for Cohort 2.
Defined Analysis Data Sets	Description
Analysis set for primary estimand (Cohort 1)	All Cohort 1-treated participants. Participants who discontinued study intervention and/or received prohibited concomitant medications prior to Week 12 will be considered non-responders.
Analysis set for primary estimand (Cohort 2)	All Cohort 2-treated participants. Participants who discontinued study intervention and/or received prohibited concomitant medications prior to Week 26 will be considered non-responders.

10.4 Statistical Analyses

Detailed methodology for the summary and statistical analyses of the data collected in this study will be documented in an SAP, which will be written and finalized prior to the study database lock. The plans outlined in this protocol may be modified in the SAP; however, any major modifications of the key endpoint definitions and/or related analyses will also be reflected in a protocol amendment.

10.4.1 General Considerations

Baseline is defined as the last observed measurement prior to the first dose of study intervention on Day 1.

In general, descriptive summaries will be presented for the efficacy and safety variables collected. Continuous variables will be summarized using the number of participants (n), mean, standard deviation, minimum, median, and maximum. Categorical variables will be summarized using frequency counts and percentages, and 95% CIs. Analyses will be performed separately for each cohort, unless otherwise stated.

10.4.2 Disposition, Demographics, and Baseline Characteristics

Participant disposition, including the number of participants screened and dosed, will be summarized for the enrolled population. Participant demographics will be summarized for the treated population and will include age, sex, race, ethnicity, height, weight, and body mass index.

Baseline characteristics will be summarized for the treated population and will include age at UC symptom onset, age at UC diagnosis, years since UC symptom onset, years since UC diagnosis,

prior anti-TNF use, corticosteroid use at screening, concomitant UC medication use at baseline, each component of the Mayo score, the complete Mayo score, the partial Mayo score, and the 9-point Mayo score.

10.4.3 Primary Endpoint

The primary endpoint for each cohort, their corresponding descriptions, and prespecified time points are listed in Table 10.4.3-1.

The primary endpoint for Cohort 1 is the proportion of participants who achieve a clinical response at Week 12. The clinical response rate at Week 12 will be estimated, and the corresponding 95% CI will be derived based on the Clopper Pearson method.

The primary endpoint for Cohort 2 is the proportion of participants who achieve a clinical response at Week 26. An estimate of the clinical response rate at Week 26 will be provided, along with the corresponding 95% CI derived based on the Clopper Pearson method.

For proportion-based efficacy endpoints, patients with missing Week 12 efficacy data from Cohort 1 and/or participants with missing Week 26 efficacy data from Cohort 2 will be considered non-responders, and non-responder imputation will be used. Sensitivity analyses around missing data may involve missing data imputed using multiple imputation and may analyze observed cases with no imputation. Details of the sensitivity analysis will be provided in the SAP.

For continuous efficacy endpoints, observed cases will be analyzed with no imputation.

Table 10.4.3-1: Endpoints

Primary	Description	Timeframe
Clinical Response (modified Mayo score)	Proportion of participants achieving the following: 
Decrease from baseline in the modified Mayo score of ≥ 2 points, andDecrease from baseline in the modified Mayo score of $\geq 35\%$, andDecrease in RB subscore of ≥ 1 point or absolute RB subscore ≤ 1.	Week 12 (Cohort 1) Week 26 (Cohort 2)
Secondary	Description	Timeframe
Clinical Remission (modified Mayo score)	Proportion of treated participants achieving the following in each component of the modified Mayo score: 
SF subscore ≤ 1, with ≥ 1-point decrease from baseline, andRB subscore = 0, andES ≤ 1.	Week 12 (Cohort 1) Week 26 (Cohort 2)
Endoscopic Response	Proportion of treated participants with a decrease from baseline of ≥ 1 point in Mayo ES	Week 12 (Cohort 1) Week 26 (Cohort 2)
Endoscopic Improvement	Proportion of treated participants with Mayo ES ≤ 1	Week 12 (Cohort 1) Week 26 (Cohort 2)

Table 10.4.3-1: Endpoints

Endoscopic Remission	Proportion of treated participants with Mayo ES = 0	Week 26 (Cohort 2)
IBDQ Response	Proportion of participants with a change from baseline in total score of ≥ 16 points	Week 12 (Cohort 1)
		Week 26 (Cohort 2)
IBDQ Remission	Proportion of patients with a total score ≥ 170 points	Week 12 (Cohort 1)
		Week 26 (Cohort 2)
Corticosteroid-free Clinical Remission (modified Mayo score)	Proportion of treated participants with: 
• Clinical remission (modified Mayo score) and• No oral systemic steroid use in prior 90 days	Week 26 (Cohort 2)
HEMI	Proportion of participants with endoscopy subscore of ≤ 1 point and a Geboes index score < 3.1	Week 26 (Cohort 2)

HEMI, histo-endoscopic mucosal improvement.

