5 STUDY DESIGN

5.1 Overall Design

Study IM047029 is a Phase 4, prospective, non-randomized, open-label, multicenter clinical study designed to explore the safety, efficacy, effects on QOL, and biomarker response of ozanimod 0.92 mg QD PO administration in participants with moderate to severely active UC in clinical practice.

This clinical study will evaluate ozanimod 0.92 mg QD PO in multiple UC disease subtypes, and with 2 specific cohorts as described in [Section 3.1](#) and [Figure 5.1-1](#).

Participants will undergo screening evaluations to determine eligibility as indicated in the SOA; see [Table 2-1](#)). Participants must meet the eligibility criteria outlined in [Section 6](#) in order to enter the treatment period. Participants must have moderate to severely active UC, defined as a score of 4 through 9 on the 9-point modified Mayo score, in order to enter the treatment period.

Assessments of medical and UC disease history, prior medications, concomitant and UC medications, tobacco/e-cigarette use, baseline (prior to flare) SF, physical examinations, 12-lead electrocardiograms (12-lead ECGs), blood, stool, and urine sample collections, endoscopies with biopsies, Physician's Global Assessment (PGA) ratings, PRO and HRQOL instruments, and other study procedures will be performed as indicated in the SOA ([Table 2-1](#), [Table 2-2](#)). Additional risk-based assessment of cardiac conduction abnormalities, pulmonary function, and/or visual

acuity (including evaluation of the fundus and macula) may also be performed during screening and as appropriate thereafter.

Disease activity assessment for the purpose of eligibility and evaluation of the primary endpoints in both cohorts will be performed using the modified Mayo score instrument ([APPENDIX 3](#)). The modified Mayo score will be calculated using data from the following sources: baseline (prior to flare) SF (patient-reported and recorded by the investigator), daily assessments of SF and RB (PROs recorded in the participant's electronic daily diary), and assessment of mucosal inflammation at endoscopy. The PGA of disease activity (physician-reported) will also be captured at various time points ([Table 2-1](#), [Table 2-2](#)).

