- 4) Agreement to be accountable for all aspects of the work in ensuring that questions related to the accuracy or integrity of any part of the work are appropriately investigated and resolved.

Those who make the most significant contributions, as defined above, will be considered by the Sponsor for authorship of the primary publication. Sub-investigators will generally not be considered for authorship in the primary publication. Geographic representation will also be considered.

Authors will be listed by order of significant contributions (highest to lowest), with the exception of the last author. Authors in first and last position have provided the most significant contributions to the work.

For secondary analyses and related publications, author list and author order may vary from primary to reflect additional contributions.

Participants must be informed that their study-related data (including but not limited to), such as endoscopy images, may be used for the publication of results, if required.

**APPENDIX 3 SELECTED INSTRUMENT DEFINITIONS (BASED ON
PERMUTATIONS OF THE MAYO SCORE)**

Modified Mayo Score	Sum of the following components of the Mayo score (Range 0-9): 
• SF subscore: Range 0-3• RB subscore: Range 0-3• ES: Range 0-3 ES is modified from the original description: Friability is not included in ES = 1.
Partial Mayo Score	Sum of the following components of the Mayo score (Range 0-9): 
• SF subscore: Range 0-3• RB subscore: Range 0-3• PGA: Range 0-3

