APPENDIX 6 SELECTED ENDPOINT DEFINITIONS

Clinical Response (modified Mayo score, primary endpoint)	Achieving the following changes from baseline in the modified Mayo score: 
• A decrease from baseline in the modified Mayo score ≥ 2 points, and• A decrease from baseline in the modified Mayo score $\geq 35\%$, and• A decrease from baseline in RB subscore ≥ 1 point or absolute RB subscore ≤ 1.
Clinical Remission (modified Mayo score)	A modified Mayo score with the following: 
• SF subscore ≤ 1, with ≥ 1 point decrease from baseline, and• RB subscore = 0, and• ES ≤ 1
Clinical Remission (partial Mayo)	Partial Mayo score ≤ 2.5
Endoscopic Response	A decrease from baseline of ≥ 1 point in Mayo ES
Endoscopic Improvement	Mayo ES ≤ 1

Endoscopic Remission		Mayo ES = 0
Histological Improvement	•	• Achieving a Geboes score < 3.1
Histologic Remission		Achieving Geboes score < 2
HEMI		Mayo ES \leq 1 and a Geboes score < 3.1
Corticosteroid-free Clinical Remission (modified Mayo score)		Clinical remission (by modified Mayo criteria), and no oral systemic steroid use in prior 90 days.
Corticosteroid-free Clinical Remission (partial Mayo score)		Clinical remission (by partial Mayo criteria), and no oral systemic steroid use in prior 90 days.

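### A missed endoscopy alone makes a participant a primary non-responder, even when the observed stool-frequency and rectal-bleeding scores settle that the response criteria are met

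*Combined protocol and SAP*

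**What the plan says.** For proportion-based endpoints, protocol section 10.4.3 counts "patients with missing Week 12 efficacy data from Cohort 1" as non-responders, and likewise "participants with missing Week 26 efficacy data from Cohort 2 will be considered non-responders, and non-responder imputation will be used". It does not say what happens when one component of a score is missing and the others are present. Multiple imputation and observed-case analyses are named as possible sensitivity analyses, with details left to the SAP.

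Appendix 3 defines the modified Mayo score as a "Sum of the following components of the Mayo score (Range 0-9"), made up of stool frequency (SF), rectal bleeding (RB) and ES, each scored 0 to 3. Under section 5.1, SF and RB come from the electronic diary and ES comes from the "and assessment of mucosal inflammation at endoscopy" part of the data. Table 2-1 schedules one post-baseline endoscopy per cohort: Week 12 in Cohort 1, Week 26 in Cohort 2.

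Clinical response (section 10.4.3 and Appendix 6) needs three things: "A decrease from baseline in the modified Mayo score ≥ 2 points"; a fall of at least 35%; and either an RB fall of at least 1 point or an RB of at most 1.

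Section 10.3 counts stopping study drug or taking prohibited medication before the primary visit as non-response. Section 7.7.2.1 adds colectomy or ostomy, and stopping for lack of effect. Neither lists a missed endoscopy.

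**The concern.** Non-responder imputation is a reasonable convention when the outcome is unknown. Here it also reaches participants whose outcome is known. ES is bounded at 3, so the observed SF and RB can show that all three criteria hold at every possible ES. Scoring such a person as a failure is misclassification, not caution about an unseen result.

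The people affected are still on ozanimod, have diary data and have had none of the failure events in sections 10.3 and 7.7.2.1. For them the rule measures response together with attendance at endoscopy, while the stated objective is the induction of clinical response.

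The primary output is one response rate per cohort with its Clopper-Pearson interval. There is no control arm in which the error could cancel, and the sensitivity analyses, even if done, leave the primary rate as it is.

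**Working it through.** **The plan's own figures.** Section 10.2 states "it is anticipated that at least 50% of Cohort 1 will achieve clinical response at Week 12" with 150 participants, and assumes 45% in Cohort 2 with 100. Clopper-Pearson limits for 75/150 are 41.7% to 58.3%, and for 45/100 they are 35.0% to 55.3%. Both agree with the plan. The half-widths are (58.3 − 41.7)/2 = 8.3 points and (55.3 − 35.0)/2 = 10.15 points. (Section 10.2 states 10.5 for the second, which does not match its own limits; nothing below depends on this.)

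**One participant.** Baseline SF 2, RB 2, ES 2, total 6. At the primary visit SF 0, RB 0, endoscopy missed. At the worst ES of 3 the total is 0 + 0 + 3 = 3. The fall is 3 points (at least 2), which is 3/6 = 50% (at least 35%), and RB has fallen by 2. All criteria are met at ES 3, and also at 0, 1 or 2, where the fall is larger. Section 10.4.3 records a non-response.

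**How general this is.** Section 6.1 requires SF ≥ 1, RB ≥ 1, ES ≥ 2 and a total of 4 to 9, which gives 3 × 3 × 2 = 18 baseline states. If SF and RB both reach 0, response is certain at ES 3 in 17 of the 18. The exception is 1/1/2 (total 4), where ES 3 leaves a fall of only 1 point.

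Each baseline state can be paired with 16 follow-up (SF, RB) results, giving 18 × 16 = 288 pairs:

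| Status with ES unseen | Pairs |
|---|---|
| Response at every ES from 0 to 3 | 46 |
| Non-response at every ES | 135 |
| Depends on ES | 107 |

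These are counts of combinations, not patient frequencies.

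**Direction.** A higher ES raises the total and so shrinks both the absolute and the percentage fall. The RB criterion does not use ES. Response therefore never improves as ES rises, and setting ES to 3 cannot create a false responder. Non-responder imputation can only turn responders into non-responders, so the error is zero or downward.

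**Share of responders provable from the diary (g).** The documents give no patient distribution, so I counted non-worsening follow-up patterns with equal weight (an assumption). There are 9 × 9 × 7 = 567 patterns, of which 351 are responses with full data. Of those 351, 167 remain responses with ES set to 3: 167/351 = 48%. This share depends on the weighting. Averaged over the 18 baseline states it is about 40%. For baseline totals 4 to 6 it is 27/115 = 23%, and for total 4 alone it is 0 of 8. I use 23% to 48%.

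**Size of the avoidable loss.** Let p be the planned response rate and m the share missing only the endoscopy, assumed independent of response. Then

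loss = p × m × g.

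| | m = 5% | m = 10% |
|---|---|---|
| Cohort 1 (p = 50%), g = 27/115 | 0.59 points | 1.17 points |
| Cohort 1, g = 167/351 | 1.19 points | 2.38 points |
| Cohort 2 (p = 45%), g = 27/115 | 0.53 points | 1.06 points |
| Cohort 2, g = 167/351 | 1.07 points | 2.14 points |

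For example, 50% × 5% × 27/115 = 0.59 points.

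**The case against.** The strongest reply is that this is a disclosed, conservative convention in an open-label descriptive study whose endpoint is a composite that deliberately includes endoscopy. Crediting response from unblinded, patient-reported diary scores alone gives up some of that, and it creates primary responders who count as failures on the endoscopic endpoints. That cost is real. It is limited because the rule credits only participants for whom no endoscopic finding could reverse the answer.

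Second, section 10.4.3 does not define missing efficacy data by component, and section 10.4 leaves detailed methods to the SAP. The documents contain no SAP text that narrows the rule. This stands as a caveat: the point follows the natural reading, and the SAP could settle it.

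Third, the named sensitivity analyses would help. Multiple imputation of ES, with response derived from it, would score provable responders correctly. Observed-case analysis drops them, but recovers the planned rate in expectation if missingness is independent of response. Both are optional, and neither changes the primary figure.

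A reader might also infer a larger bias: p × (1 − m), which takes Cohort 1 from 50% to 47.5% at m = 5% and 45.0% at m = 10%, and Cohort 2 from 45% to 42.8% and 40.5%. That is the loss from every missed endoscopy. It includes responders whose outcome turns on the unseen ES. For them non-response is ordinary conservative imputation, and the proposed rule keeps it. Nor do the documents support the idea that participants who feel well are the ones who decline endoscopy. Non-responders may equally skip it, which would shrink the effect.

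**Conclusion.** The point holds in a limited form. As written, the rule can score a known responder as a failure, so the primary rate can be biased downward and never upward. Whether it will be, and by how much, cannot be determined from the documents: they give no missed-endoscopy rate and no baseline mix, and the bias is zero if no provable responder misses the endoscopy.

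The figures of roughly half a point to just over 1 point at m = 5%, and 1 to 2.4 points at m = 10%, rest on three assumptions: the planned rates, missingness independent of response, and a provable share of 23% to 48%. They are well inside the half-widths of about 8 and 10 points. Sampling error does not excuse an avoidable misclassification, but the scale makes this a cheap improvement and not a threat to the study's conclusions.

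**What to change.** In section 10.4.3 and the SAP, add for the primary endpoint only: if the Week 12 (Cohort 1) or Week 26 (Cohort 2) ES is the only missing component, SF and RB are available, and no failure under section 10.3 or 7.7.2.1 has occurred, set ES to 3 and apply the response criteria. The participant is a responder if all are met and a non-responder otherwise.

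Keep non-responder imputation for all other missing data and for every endpoint that needs an observed ES (clinical remission, the endoscopic endpoints and histo-endoscopic mucosal improvement). Report how many participants are classified by this rule in each cohort, and give the strict non-responder-imputation rate as a sensitivity result.

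The cost is a sentence or two of text and a few lines of derivation code, with no new data. The drawback is that a few primary responders will have no endoscopic reading and will count as failures on the endoscopic endpoints; the reported count makes this visible. The rule should be fixed before database lock. Section 10.4 requires a protocol amendment if the change is judged a major modification of a key analysis.
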